~33	6-Month Follow-Up Assessment	Clinical interview, immediate treatment interview, & self-report battery (7 measures), treatment satisfaction

Note. Behavior therapy involves the introduction, teaching, in-session and between-session practice, and mastery of behavioral therapeutic techniques designed to improve symptoms of depression and anxiety, including behavioral activation (BAT group) as well as situational, physical, thought, and emotional exposures (transdiagnostic CBT group). Final treatment session will take place between sessions 12-16, as determined by provider and participants' collective decision. Final treatment session will involve relapse prevention content. Post-treatment assessment will be completed 1 week immediately after final treatment session. 6-month follow-up assessment will be completed 6-months after final treatment session.

Randomization Procedures

Participants will be randomly assigned (1:1) to one of the two study arms (*n* = 48 per arm) using a permuted block randomization procedure. Randomization will be stratified by principal diagnostic group and block size will be varied to minimize the likelihood of unmasking. After determining eligibility and completing consent and baseline assessment materials, enrolled participants will be assigned to treatment groups by the Project Research Assistant using a computer generated randomization scheme. Once a participant is randomized and attends the first session, they will be included in the intent-to-treat analysis. Randomization will occur at the participant level. As such, we will take the following steps to minimize contamination between the two arms of the study: 1) only one member of a household will be eligible for enrollment; and 2) other VAMC providers will be informed of their patients' participation in the study, but will be blinded to the treatment condition of their patients.

Transdiagnostic CBT Treatment Condition

As noted above in the Preliminary Studies section, a transdiagnostic CBT protocol was developed and revised through two demonstration studies and one focus group. The resulting protocol involves several primary components, including psychoeducation on the symptoms of depression and anxiety (session 1), assessment of motivation and setup of treatment plans (session 2), exposure therapy (sessions 3-15), and relapse prevention (final session). In addition to these primary components, optional modules are included to supplement exposure

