The full battery of self-report questionnaires and a diagnostic interview will be completed pre-treatment, immediate post-treatment, and at the 6-month follow-up to track participants' progression through treatment and maintenance. These time points for the assessments are consistent with CBT research with Veterans with depressive/anxiety disorders. To reduce the likelihood of missing data, all assessments will be scheduled separately from normal treatment sessions (intake appointment, one week following the final treatment session, and at 6-month follow-up). Additional staff training will be required prior to administration of the diagnostic interview. All assessments will be completed by the Project Research Assistant. All assessment staff will be required to observe the Principal Investigator administer the test twice and then administer the test twice themselves under the direct observation of the PI. All assessment staff will be blinded to treatment condition and supervised by the Principal Investigator. Assessments will be recorded to investigate inter-rater reliability. In addition to the pre- and post-treatment and follow-up assessments with the full battery, a brief assessment involving a few self-report measures (e.g., Depression Anxiety Stress Scales, Illness Intrusiveness Rating Scale, and State-Trait Inventory for Cognitive and Somatic Anxiety) will be completed biweekly to monitor symptoms during the course of treatment.

Albany Panic and Phobia Questionnaire (APPQ). The APPQ is a 27-item self-report measure that assesses agoraphobia, social anxiety, and interoceptive avoidance. Each subscale has been shown to have good internal consistency (α s > .85) and temporal stability (rs > .87).

Anxiety Disorder Interview Schedule-5 (ADIS-5). The ADIS-5 is a well-established, semi-structured interview designed to assess a wide range of Axis I disorders. The ADIS-5 assesses current and past diagnoses with DSM

diagnostic criteria, severity scores, and lists of feared and avoided situations for the anxiety disorders. The ADIS has demonstrated excellent inter-rater reliability and validity of depressive/anxiety disorder diagnoses.

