The full intent to treat (ITT) analysis set will comprise all randomized participants. Missing data in the full analysis set will occur if participants drop out prior to the end of the study. Participants will not be discontinued from the study because of non-adherence and all will remain in the study unless consent is withdrawn or if there are concerns regarding participant safety. Missing data for the ITT analysis set will be imputed using multiple imputation methods. The results of analyses using study completers and protocol adherers (completer and perprotocol analyses) will be compared with results using the ITT analysis set to test sensitivity of study conclusions to study drop-outs and protocol non-adherence. In addition, the information on dropout proportion will be used as one of the outcome measures of intervention feasibility.

Efficacy (Symptomatology & Quality of Life) Measures Analyses (Primary Aim 1)

The continuous measures of intervention efficacy and quality of life are APPQ, DASS, IIRS, MASA, PCL, STICSA, and V/SF-36. The primary outcome time point is at the end of the active intervention phase (immediate post-treatment) and the secondary time point is at the end of the naturalistic 6-month follow-up period. The difference in mean change from baseline to end-of-active intervention (effect sizes) for transdiagnostic CBT versus BAT control condition will be estimated via 95% CI. For the secondary time-point analyses, transdiagnostic CBT versus BAT control differences in change from immediate end-of-intervention to the 6-month follow-up will also be estimated using 95% CI. By assessing the magnitude of the between-intervention-group differences, as described by the CI, clinicians can judge whether the novel intervention provides sufficient improvement in these outcomes to suggest a clinically significant result that warrants further investigation.

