Measures of feasibility and acceptability are dropout proportions (dropout y/n), proportion of sessions attended, proportion of homework assignments completed, and patient satisfaction scores on the STTS-R. 95% CI for proportions will be used to estimate the proportion of participants who exit the study prematurely (drop out) within each intervention group and the difference in dropout proportions between the intervention groups. For the treatment satisfaction and adherence outcomes (STTS-R, proportion of missed sessions or homework assignments), the median and mean responses will be obtained within and between each intervention group. 95% CI for difference in means will be used to estimate the between intervention differences in treatment satisfaction (mean STTS-R) and adherence (e.g. average proportion of missed sessions or homework assignments) for the transdiagnostic CBT versus BAT control conditions. Frequency distributions describing the participants' reasons for noncompliance and discontinuation of participation will be developed.

The GLMM modeling framework described for Primary Aim 1 will be used to compare the effect of transdiagnostic CBT versus BAT control on treatment satisfaction, retention (dropout), and treatment adherence (% missed sessions, % homework completion). Dropout proportions (dichotomous outcome) and % of missed visits and % homework completion will be compared between the intervention groups using GLMM, with logistic/binomial regression analyses as special cases for dichotomous and percentage outcomes; STTS-R will be modeled as a continuous outcome using an appropriate link function. We also will model the longitudinal profile of adherence as a dichotomous outcome at each visit (e.g. attended/did not attend a given session). This will allow us to evaluate the trends in session attendance and to determine if the trends differ by intervention (e.g. whether the probability of missing visits is less/greater at earlier or later time points).

Exploratory Analyses - Diagnostic Groups

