There is a potential psychological risk of emotional discomfort during the assessment and treatment procedures. Although this reaction is not uncommon in exposure-based treatments of anxiety and depression and typically is brief in its duration, there are several provisions to reduce and/or avoid it in the proposed study. First, the proposed treatment will be designed specifically to target the reduction of emotional distress, anxiety, and avoidance. Second, if a participant expresses a desire to discontinue treatment due to distress and/or a study clinician determines that participation is counter-indicated, all research and treatment procedures will be terminated.

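### Stopping treatment because of distress also ends all assessments, which conflicts with the plan's own rule on who stays in the study

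*Combined protocol and SAP*

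**What the plan says.** Section E.1.c (Potential Risks) names the psychological risk as "emotional discomfort during the assessment and treatment procedures" and gives a stopping rule. It applies when a participant "expresses a desire to discontinue treatment due to distress", or when a study clinician finds participation counter-indicated. The two triggers are joined by and/or, so either is enough. The consequence is that "all research and treatment procedures will be terminated".

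The Missing Data section says that non-adherence is no reason to discontinue anyone, and that "all will remain in the study unless consent is withdrawn or if there are concerns regarding participant safety". It defines the ITT set as all randomized participants and imputes their missing data by multiple imputation. Randomization Procedures words the set differently: "Once a participant is randomized and attends the first session, they will be included in the intent-to-treat analysis".

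On outcomes, the efficacy section states: "The continuous measures of intervention efficacy and quality of life are APPQ, DASS, IIRS, MASA, PCL, STICSA, and V/SF-36". The primary time point is immediate post-treatment; 6 months is secondary. The Primary Aim 2 analyses estimate "between intervention differences in treatment satisfaction (mean STTS-R") and adherence. In the table of procedures, the full battery after baseline and the satisfaction measure are scheduled only at the post-treatment and 6-month visits. A brief battery (DASS, IIRS and STICSA are named) "will be completed biweekly to monitor symptoms during the course of treatment".

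**The concern.** A wish to stop therapy is not a wish to leave the study. The Protection against Risk list treats withdrawal from the study as a separate right. A participant may find therapy too distressing, be in no danger, and be willing to fill in questionnaires some weeks later. The Missing Data section keeps that person; the Potential Risks section ends their assessments. Staff could therefore handle identical participants differently.

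If the Potential Risks rule is followed, outcomes at the primary time point are missing for a reason tied to treatment. Satisfaction is also missing from people whose experience bears directly on the tolerability claim in Hypothesis 2. Imputation can fill such gaps but cannot recover what was never asked.

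**Working it through.** **1. The rules side by side**

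| Place | Trigger | Consequence |
|---|---|---|
| Potential Risks, participant branch | Wants to stop treatment because of distress | Treatment and research both end |
| Potential Risks, clinician branch | Participation counter-indicated | Treatment and research both end |
| Missing Data | Consent withdrawn, or safety concern | Leaves the study; all others stay |
| Protection against Risk, item 2 | Appears unable to tolerate assessment | Study procedures end |

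The clinician branch and any unsafe case fit the safety exception under Missing Data. Intolerance of assessment has its own rule. What remains is the participant who stops therapy because of distress, raises no safety concern and still consents. Having started treatment, that person is in the ITT set under either wording.

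**2. What is lost and what survives for that person**

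- Lost: post-treatment and 6-month scores on all seven efficacy measures, and STTS-R.
- Available for imputation: biweekly DASS, IIRS and STICSA up to the stop. APPQ, MASA, PCL and V/SF-36 have only the pre-treatment score. STTS-R has no earlier score at all. The imputation model is not specified.
- Kept: dropout status, attendance up to the stop, and reasons for discontinuation.
- Unaffected: the feedback interviews, which are already limited to transdiagnostic CBT completers.

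**3. The plan's only attrition figure**

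The target is 96 randomized with at least 72 completers. Implied non-completion is 1 - 72/96 = 25%, or 24 people; conversely 72/(1 - 0.25) = 96. This checks consistency only, since the 25% comes from the same two numbers. The pilots agree: 12/15 = 80.0% and 23/31 = 74.2% completed, pooled 35/46 = 76.1%.

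None of these figures isolates distress. If 10%, 25%, 50% or 100% of the 24 non-completers stopped for distress (assumed), that is 2.4, 6, 12 or 24 people.

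**4. Bias in the treatment difference**

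Bias in SD = pCBT x dCBT - pBAT x dBAT. Here p is the share of the 48 in an arm lost under this rule, and d is how much worse, in SD, the true outcome is than the imputed one. A positive value favours CBT. Every p and d below is assumed.

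| Lost, CBT vs BAT | d, CBT vs BAT | Bias (SD) |
|---|---|---|
| 3 vs 3 | equal | 0 |
| 3 vs 3 | 0.8 vs 0.4 | 3/48 x 0.8 - 3/48 x 0.4 = 0.025 |
| 3 vs 3 | 0.8 vs 0 | 3/48 x 0.8 = 0.050 |
| 5 vs 1 | 0.8 vs 0.8 | 5/48 x 0.8 - 1/48 x 0.8 = 0.067 |
| 5 vs 1 | 0.4 vs 0.4 | 5/48 x 0.4 - 1/48 x 0.4 = 0.033 |
| 5 vs 1 | 0.16 vs 0.8 | 5/48 x 0.16 - 1/48 x 0.8 = 0 |
| 5 in one arm, no contribution from the other | 0.8 | 5/48 x 0.8 = 0.083, either sign |

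**5. Against sampling error**

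With 36 per arm (72 completers split equally), the standard error of a difference in means is sqrt(2/36) = 0.236 SD, and 0.083/0.236 = 0.35. With all 48 per arm it is sqrt(2/48) = 0.204 SD, and 0.083/0.204 = 0.41.

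The 0.083 is not a bound. If the arms differ by 2 to 15 percentage points in these losses and d is 0.25 to 1.0 in both arms, the bias runs from 0.02 x 0.25 = 0.005 to 0.15 x 1.0 = 0.15 SD. The top value is 0.15/0.236 = 0.64 of a standard error.

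**6. What the change could recover**

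If half of those lost would attend when invited (assumed), about half the bias goes: 0.083/2 = 0.042 SD at the extreme in the table. The effect on STTS-R was not quantified.

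**The case against.** **Distress may be a safety concern.** The stopping rule sits in a section on risks, so it can be read as an instance of the safety exception rather than a conflict with it. This fits poorly with the rest of the protocol. Potential Risks calls the reaction not uncommon and usually brief. Protection against Risk retains participants who have suicidal ideation without intent. The Data and Safety Monitoring Plan offers other treatment after a 25% worsening at two consecutive assessments and does not say that research ends. Even on this reading, the participants stay in the ITT set without outcomes.

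**The plan may already support continued assessment.** The Missing Data section, read alone, does so, and Sources of Materials says that participants will be asked to complete the assessments three times. This stands. The defect is a conflict between two rules, not the absence of any basis for follow-up.

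**Ending assessments protects participants.** The section does mention discomfort during assessment. But its participant trigger is the wish to stop treatment, and assessment intolerance is covered elsewhere. An invitation can be declined.

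**Dropout is anticipated.** Multiple imputation, completer and per-protocol comparisons and a tabulation of reasons are all planned. They manage the gap without filling it. The completer and per-protocol sets leave out early stoppers, and no missing-not-at-random analysis is described.

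**The size is assumed and small, and the trial calls itself preliminary.** This stands too, and it limits how much weight the point can bear.

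**Conclusion.** The conflict is real and narrow. If the Potential Risks rule is followed, participants who stop for distress, raise no safety concern and still consent give no post-treatment or 6-month scores and no STTS-R, although they remain in the ITT set. On the inputs tabulated above, the efficacy bias lies between -0.083 and +0.083 SD; the wider assumptions reach 0.15 SD. No input for losses or outcome shifts comes from the documents, so these are illustrations, not estimates.

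A reader might infer more in three ways, and the documents do not support any of them.

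- **That the rule flatters transdiagnostic CBT because exposure provokes distress.** Potential Risks does link distress to exposure-based treatment, and exposure belongs to the CBT arm. But no rate by arm is given, Hypothesis 2 predicts better dropout with CBT, and bias also depends on how far imputed values miss in each arm. The direction is unknown.
- **That all information on early stoppers is lost.** Dropout, attendance, reasons and the biweekly scores before the stop remain.
- **That the primary comparison is unreliable because of this rule.** At the sizes above, the bias is below one standard error.

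The case for change is that it is cheap and that uncollected scores cannot be recovered later. It is a worthwhile improvement rather than an essential correction.

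**What to change.** Amend Potential Risks so that stopping because of distress ends treatment only. Participants who do not withdraw consent are then invited to the post-treatment and 6-month assessments, including STTS-R. Keep the safety exception under Missing Data, the clinician branch, the assessment-intolerance rule, and the right to stop treatment or withdraw.

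The note to the table of procedures counts both visits from the final session, so early stoppers need one stated anchor. For example, hold post-treatment at about week 18 and follow-up six months after the planned end of treatment. Write the follow-up date out: the table's week of about 33 is only 33 - 18 = 15 weeks after week 18. State that these scores enter the ITT analysis whether or not the participant has since had non-study care.

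The cost is protocol wording, a few extra contacts, and assessor time for an interview and questionnaire battery per attender. Assessments are already scheduled apart from therapy sessions. The main downside is some assessment burden on people who stopped because of distress, who may decline.

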2. ADEQUACY OF PROTECTION AGAINST RISKS

a. Recruitment and Informed Consent

VAMC patients will be recruited from within the Primary Care Mental Health Integration psychotherapy program and CBT Clinic at the RHJ VAMC. All eligible and willing VAMC patients will be required to meet with project staff to review the purpose of the study and review the consent documentation. VAMC patients will be given ample time to discuss the study and ask questions regarding the procedures. Upon thorough review of all documentation, VAMC patients will sign the informed consent document prior to participation in study procedures.

- b. Protection against Risk
- 1. Participants will be made aware of the potential risks and benefits associated with participation and their right to withdraw from the study at any point without any negative impact on their care within the VAMC. Any participants expressing interest in withdrawing from the study will be referred for treatment within the VAMC.
- 2. Participants who appear unable to tolerate the assessment process will be offered a referral to the VAMC and terminated from the study procedures.
- As a member of the mental health service at the VAMC, the Principal Investigator will maintain active collaborations and communications with other VAMC providers to ensure appropriate continuity of care and safeguard against any adverse events.
- 4. All assessors and treatment providers will be trained and supervised by the Principal Investigator, who is a licensed psychologist. At intake, participants identified by clinical interview with both suicidal ideation and acute intent will be excluded from the study and immediately offered emergency psychiatric care at the VAMC. During the duration of the study, the Principal Investigator immediately will contact the participant and assess suicide risk when any instance of suicide risk is identified. If suicidal ideation is present but not intent, the participant will be retained in the study and reassessed for suicide risk by the investigators in one week. In cases of acute suicidal intent, state law requires immediate hospitalization and these guidelines will be followed.
- 5. Treatment progress will be assessed throughout the active treatment phase through participant interactions with the project therapist as well as biweekly self-report measures of various psychiatric symptoms (e.g., DASS, IIRS, & STICSA). Participants who do not respond adequately to either treatment will be offered mental health treatment with an appropriate VAMC provider.
- 6. All adverse events associated will be reported to CSR&D program officers and relevant IRBs.
- 7. All participants will be informed if significant information is discovered about the treatment or if other more effective treatment interventions are discovered.
- 8. Published works or presentations will be limited to aggregate findings; individuals will not be mentioned or identified. All participants will be linked by their social security number and then assigned a research identification number to de-identify the master database for data analyses. Copies of research identification numbers and social security numbers will be stored separately as will consent documentation and assessment and treatment instruments. All paper materials will be stored in locked file cabinets. Access to all research records will be restricted to project staff.
- 9. All project staff will undergo training in the protection of human subjects, including the DVA's Good Clinical Practice and the Miami University CITI course.

3. POTENTIAL BENEFITS OF THE PROPOSED RESEARCH TO THE SUBJECTS AND OTHERS

There are several potential benefits of the proposed research. First and foremost, a large number of VAMC patients with depressive/anxiety disorders will participate in an evidence-based psychosocial treatment, resulting in reduced symptomatology and improved quality of life. Second and more broadly, a new transdiagnostic psychotherapy will be evaluated in VAMC patients with depressive/anxiety disorders that likely will improve access to these services in the VAMC system. Thus, the risk-benefit ratio is in favor of conducting this research.

4. IMPORTANCE OF THE KNOWLEDGE TO BE GAINED

Psychosocial treatments for the depressive/anxiety disorders are greatly limited in the DVA. The limitation may be a result of number of factors, including both VAMC provider and VAMC patient factors. Given the high prevalence of depressive/anxiety disorders in the DVA, the development and evaluation of a new treatment designed to treat VAMC patients with transdiagnostic presentations of depressive/anxiety disorders will represent an opportunity to improvement services and increase access for this population and outweigh the potential risks discussed above.

5. SUBJECT SAFETY AND MINIMIZING RISKS (Data and Safety Monitoring Plan)

The proposed investigation includes a clinical trial that involves the comparison of a newer evidence-based psychotherapy, transdiagnostic CBT, with an established evidence-based psychotherapy, BAT. Both treatment conditions involve active treatments have been shown to be effective in addressing symptoms in the selected disorders/population. Several steps were included in the proposed clinical trial for subject safety and minimizing risks of the research.

- 1. Treatment progress will be assessed throughout the active treatment phase (baseline to final session of psychotherapy) through participant interactions with the project therapist, self-monitoring and other between session exercises, biweekly self-report measures of various psychiatric symptoms (e.g., DASS, IIRS, & STICSA), and immediate post-treatment assessment. Participants who demonstrate worsening of symptoms at any point in treatment (i.e., 25% increase in symptom severity for two consecutive assessment points) or do not demonstrated any symptoms improvement at the midway point in treatment (session 8) will be offered alternative mental health treatments with appropriate VAMC providers. Similarly, alternative mental health treatments with appropriate offered at the 6-month follow-up assessment point to all participants, regardless of symptomatology.
- During the active treatment phase, participants will be monitoring weekly during their psychotherapy appointments. Monitoring will involve interactions with the project therapist, self-monitoring and other between session exercises, and biweekly self-report measures of various psychiatric symptoms (e.g., DASS, IIRS, & STICSA).
- 3. Monitoring will be completed by the project therapist and reviewed by the Principal Investigator during weekly supervision meetings.
